STUDY20010059 – Title Validation of a novel foot offloading device

Clinical Trials.gov number- NCT04378270

IRB protocol approval- 12/10/2021

Principal Investigator- [name]

Date: Wednesday, September 21, 2022 10:17:12 AM

Print

Close

View: Pitt SF: Basic Study Information 8.2

Basic Study Information

11 -	ж	Title of s	tudy:

Validation of a novel foot offloading device

2. * Short title:

Validation of a novel foot offloading device

3. * Brief description:

Pressure offloading is often considered the most crucial aspect in healing after a foot injury. The investigators have devised a novel foot offloading device (PopSole™) which will allow for customization of the area where there is foot pain, as well as allow for customizable arch support and elevation of the metatarsals. This validation study is aimed to assess improvement of pain with use, ease of use, fit and feel, compliance, and durability over a 4 week period. Validated patient reported outcome measures will be used at baseline, 2 weeks and 4 weeks.

4. * What kind of study is this?

Single-site study

5. * Will an external IRB act as the IRB of record for this study?

0	Yes	No

6. * Local principal investigator:

[name]

* Is this your first submission, as PI, to the Pitt IRB?

0	Yes	0	No

7. * Does the local principal investigator have a financial interest related to this research?

0	Yes	No

8. Attach the protocol:

- Sponsor/Multicenter/Investigator-initiated protocol
- Coordinating Center supplement
- Emergency Use Consent/ Protocol/ FDA Form 3926
- Exempt Application form

Document Category Date Modified Document History
There are no items to display

View: Pitt SF: Funding Sources (not integrated with Grants)

Funding Sources

* Indicate all sources of support: Internal funding

2. * Provide the source of your Internal funding:

A Coulter Translational Research Partners II Program Grant from the University of Pittsburgh Department of Bioengineering

Study Team Members

1. * Identify each person involved in the design, conduct, or reporting of the research (includes PI):

Name	Roles	Department/Schoo	Affiliation	Involved in	Qualifications
				Consent	
[name]	Principal Investigator	U of Pgh School of Medicine Plastic Surgery	Pitt faculty	yes	[name] is a plastic surgeon at UPMC who specializes in foot fat grafting. He has expertise in advising patients how to offload these re view all

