week study including an in-person baseline visit, 2-week visit, and a final 4-week visit. The subject will be reimbursed using the UPMC "Vincent" system at the time of each visit. All participant reimbursement will be provided through Vincent Payment Solutions processing.

This applies for cohort 2. \$100 will be offered to participants who complete the 3-month study including \$25 for the one-month visit, \$25 for the two-month visit, and \$50 for the final three-month visit. The subject will be reimbursed using the UPMC "Vincent" system at the time of each visit. All participant reimbursement will be provided through Vincent Payment Solutions processing.

5. Recruitment materials: (attach all material to be seen or heard by subjects, including advertisements and scripts)

Document Category Date Document Modified History

Insole Flyer Recruitment 2/26/2020 History 02.26.20_Version_0.01.doc(0.02) Materials

view PopSole2 Telephone Script(0.02) Recruitment 2/11/2020 History

View: Pitt SF: Study Aims

Study Aims

1. * Describe the purpose, specific aims, or objectives and state the hypotheses to be tested:

The investigators will perform a prospective validation study utilizing PopSole™, a novel fully customizable shoe insert, to assess the relief of foot pain. We will assess the fit, feel, ease of use, and durability of the device.

Aim 1: We aim to evaluate a novel foot offloading device for patients with foot pain to decrease pain and improve activities of daily living. This will be achieved through questionnaire and survey collection for patient reported outcome measures.

Aim 2: We aim to demonstrate ease of use, feel, durability, and compliance with the device. A survey will be used to obtain this outcomes data. pain) when using the PopSoleTM. Validated patient reported outcome measures will be utilized.

2. * Describe the relevant prior experience and gaps in current knowledge including preliminary data. Provide for the scientific or scholarly background for, rationale for, and significance of the research based on existing literature and how it will add to existing knowledge:

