Describe the primary and secondary study endpoints:

Primary Outcomes: Pain scores as assessed by validated outcomes measures, compliance over 4 weeks, durability of the device (do the bubbles hold up or require replacement).

Secondary Outcomes: Satisfaction with using the device, difficulties with the use of the device.

4. Provide a description of the following study timelines:

Duration of an individual subject's active participation:

Cohort 1: 4 Weeks

Cohort 2: 3 Months

Duration anticipated to enroll all subjects:

6 months

Estimated date for the investigator to complete this study (complete primary analyses):

6/30/2020

5. List the inclusion criteria:

Patients meeting the following criteria will be eligible to participate in the study:

- 1. Aged 18 years or older and able to provide informed consent
- 2. Subjects with foot pain due to forefoot or heel fat pad atrophy or chronic plantar fasciitis as defined by heel pain for greater than 6 months and failed non-surgical therapy
- 3. Willing and able to comply with follow up examinations

6. List the exclusion criteria:

Patients with the following characteristics will be excluded from participating in the study:

- 1. Concurrent injury to the lower extremity that would effect gait
- 2. Open foot ulcerations, fractures, or diagnosis of osteomyelitis of the feet
- 3. Surgical foot intervention in the last 6 months
- 4. Diagnosis of pregnancy or the intent of the participant to become pregnant during participation in this study
- 5. Neuropathy

- 6. Any issue that per the physician's determination would render the patient not appropriate to continue participation in the study (compliance, change in physical status, etc.)
- 7. Will children or any gender, racial or ethnic subgroups be explicitly excluded from participation?
 - Yes O No
 - * Identify the subgroups and provide a justification:

As foot pain due to forefoot or heel fat pad atrophy or chronic plantar fasciitis generally is not common in children, we will be limiting our population to adults 18 years of age or older.

8. Describe the power analysis used and cite your method of statistical analysis. If a power analysis is not possible, thoroughly justify the sample size required for the study, including appropriate literature citation (alternatively provide page reference in attached protocol):

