Pain and activity questionnaires will be performed at 3 time points during the trial. Repeated measures analysis of variance will be used to compare change over time in foot pain, and tissue thickness. A power analysis was performed based on preliminary data collected in our previously conducted clinical trial (PRO#016030521). To meet a power of 0.8 and alpha of 95% with effect size of 1.35, at least 10 human subjects will be needed to evaluate activities of daily living at pre and 4 weeks post-op.

View: Pitt SF: Research Activities

Research Activities

1. * Provide a detailed description of all research activities (including screening and follow-up procedures) that will be performed for the purpose of this research study. This description of activities should be complete and of sufficient detail to permit an assessment of associated risks.

All the following research activities are research procedures and are being completed for the purpose of this clinical trial. The following procedures will be completed prior to the PI's determination of subject's study eligibility. All screening procedures will take place at the Isaly's Medical building - UPMC Aesthetic Plastic Surgery Center and/or Lemieux Sports Medicine Complex. The information gathered during these visits will be from a combination of subject statement, medical record review, and in-person assessments and evaluations."

Optional digital recordings (i.e. photography) may be collected from any and all portions of the subject's research visits. These may include, but not be limited to, photos of functional assessment testing and clinical exams or photos of follow-up clinical course, etc. The study team will track/log those who agree to this vs. those who do not by including a section on the informed consent. This will also be kept in a spreadsheet to prevent us from taking photographs from subjects who have not authorized this activity. In addition, at follow-up visits, before any photographs are taken, participants will be asked again for verbal consent to the photographs.

COHORT 1:

Patients presenting with foot pain (pain in the forefoot, heel or plantar fascia) will be offered inclusion in the clinical trial. Information about the study will be provided at the time of candidate review. Once informed consent has been obtained then study procedures will be implemented for eligibility determination.

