Should the subject complete the informed consent process and screening procedures, the duration of time to complete is estimated to take approximately 1-2 hours and will include the following research procedures:

- 1.) Obtain Informed Consent to be completed by the Principal Investigator (PI) or designated Co-Investigator. Once completed the subject will be allocated a subject ID number. This number will be the unique identifier for the subject during his/her trial participation.
- 2.) Performance of a limited physical exam, inclusive of participant's foot exam with a gait and shoe gear evaluation to be completed by the PI and /or Co-investigator. Any prior foot injuries or previous foot ulcerations/skin breakdown will be assessed. The foot exam will include a vascular, neurologic, dermatologic and orthopedic baseline assessment. As part of the exam (for example, related to diagnosing plantar fasciitis), an ultrasound may be performed in the clinics per the investigators' discretion.
- 3.) Medical and surgical history collection: Past medical and surgical history will be collected by referral report or subject report.

Should the physician require additional information for review to confirm study eligibility, the subject may be asked to obtain and provide medical records to assist with the PI's review.

- 4.) Collection of subject's vital signs (Temp, HR, Resp., BP), medication profile, allergies, height, weight, and BMI calculation.
- 5.) Collection of demographic information to include subject's date of birth, gender, race, ethnicity, education, and smoking history.

ELIGIBILITY DETERMINATION: The Principal Investigator and/or in consultation with the co-investigators will determine subject eligibility to participate in the study based on the inclusion/ exclusion criteria.

All subjects will receive the PopSole™ offloading device at the screening/baseline visit, be asked to wear it for 4 weeks, and will be asked to return for an in-person

evaluation at V1 (Week 2), V2 (Week 4), V3 (Week 8) and a completion study visit at V4 (Week 12). There will also be a phone call 48 hours after the screening visit, At week 6 and at Week 10 to ensure that the patient has no issues or concerns with wearing the device.

Subjects will complete the following screening research procedures:

- 1.) Baseline reported outcome measures (PROMs) questionnaires and surveys that will take approximately 25 minutes to complete:

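### The repeated-measures ANOVA named for foot pain has no rule for missed visits; in its classical form it discards observed baseline-to-Week-4 pairs and ignores Week 2 scores of people who miss Week 4

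*Combined protocol and SAP*

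**What the plan says.** Study Design item 8 names one method for the pain outcome: "Repeated measures analysis of variance will be used to compare change over time in foot pain, and tissue thickness". It introduces the data with "Pain and activity questionnaires will be performed at 3 time points during the trial". The brief description under Basic Study Information identifies the occasions: "Validated patient reported outcome measures will be used at baseline, 2 weeks and 4 weeks".

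The endpoint item of Study Design reads "Primary Outcomes: Pain scores as assessed by validated outcomes measures, compliance over 4 weeks, durability of the device", and the background section describes the primary aim as a 4-week trial of the device. The sample-size statement in item 8 is "To meet a power of 0.8 and alpha of 95% with effect size of 1.35, at least 10 human subjects will be needed". It concerns activities of daily living before use and at 4 weeks, so it involves two occasions and not pain. Planned enrolment is 20 (Study Design item 1), with no split between the two cohorts.

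The available text contains no missing-data rule, analysis set, imputation method or mixed model. The nearest statement, on withdrawal under Risk and Benefits, says that data recorded before withdrawal will continue to be used. It does not say how they enter the analysis.

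**The concern.** Classical repeated-measures ANOVA needs a value from every participant at every level of the time factor. With three levels, this has two consequences.

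- A person with baseline and Week 4 pain scores who missed Week 2 drops out. The change that the 4-week aim is about was observed for that person and is then not used.
- A person with baseline and Week 2 scores who missed Week 4 also drops out, and the Week 2 score is ignored. That score shows whether those who stopped attending were doing worse.

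The first consequence costs precision in a study of 20. The second can bias the result in favour of the device if people with little early relief are the ones who do not return. The study has a single arm, so no comparison group would show the distortion.

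**Working it through.** **1. The plan's own figure.** Inputs from item 8: power 0.80, effect size 1.35, and the stated alpha read as 0.05, taken as two-sided. An unpaired two-sample t test needs 10 per group (power 0.81 with 10, 0.77 with 9), which matches the stated 10. A paired t test, which suits a before-after comparison, needs 7 (power 0.84 with 7, 0.75 with 6). A paired 7 with a 30% dropout allowance also gives 7/0.7 = 10, but no such allowance is stated. The 10 therefore reproduces, but does not show that missed visits were provided for.

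**2. People kept.** Let m be the chance of missing each follow-up visit, independent across visits, with baseline always present. The documents give no m, so a range is shown. Of 20 enrolled:

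| m | Baseline and Week 4: 20(1−m) | All three: 20(1−m)² | Lost only for Week 2: 20m(1−m) |
|---|---|---|---|
| 5% | 19.0 | 18.1 | 0.95 |
| 10% | 18.0 | 16.2 | 1.8 |
| 20% | 16.0 | 12.8 | 3.2 |
| 30% | 14.0 | 9.8 | 4.2 |

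At m = 10%, the chance that at least one observed pair is lost is 1 − (1 − 0.09)^20 = 0.85.

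**3. What software does.** In simulated data on 20 people, 4 of them missing Week 2 only, a standard repeated-measures ANOVA routine (statsmodels) rejected the data as unbalanced and ran only on the 16 complete cases. A mixed model used all 20 people and 20×3 − 4 = 56 observations.

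**4. Power.** Paired t test, two-sided 0.05, noncentral t with noncentrality d√n:

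| d | n = 20 | n = 18 | n = 16 | n = 13 |
|---|---|---|---|---|
| 1.35 (plan) | >0.99 | >0.99 | 0.999 | 0.994 |
| 0.66 (assumed) | 0.80 | 0.75 | 0.69 | 0.59 |

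The value 0.66 is not in the documents. It is the standardised change that 20 pairs detect with 80% power. At m = 10% the cost of the method is the step from 18 to 16 people, 0.75 to 0.69. The step from 20 to 18 reflects missing Week 4 scores.

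**5. Bias.** Assumed set-up: no true change at Week 4; unit-variance scores with correlations 0.6 (baseline, Week 2), 0.5 (baseline, Week 4) and 0.7 (Week 2, Week 4); higher score means more pain. The log-odds of missing Week 4 rise by b for each SD of worse baseline-to-Week-2 change, and the intercept is set to give the stated proportion missing.

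| Week 4 missing | b = 0.5 | b = 1 | b = 2 |
|---|---|---|---|
| 15% | 0.05 | 0.09 | 0.14 |
| 25% | 0.08 | 0.14 | 0.21 |

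Entries are the spurious improvement among completers, in SD of the score. The likelihood-based estimate using everyone's Week 2 score was 0.00 in every cell. For scale, the SD of the change here is √(2 − 2×0.5) = 1, so with 16 completers the standard error is 1/√16 = 0.25. A bias of 0.1 to 0.2 is then 0.4 to 0.8 of a standard error.

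**The case against.** The strongest reply is that the plan nowhere says incomplete participants will be excluded, and that the term repeated-measures ANOVA is sometimes used loosely for a mixed-model fit. This stands as a limit. A reader might infer that exclusion is the stated rule. It is only what the named method does in its classical form when nothing else is specified. If a mixed model was intended, the plan should say so.

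The reply on power is also largely right. At 1.35, even 13 completers give power of 0.99, and 13 exceeds the stated minimum of 10. A reader might quote a fall from 0.80 to 0.69, but that compares 20 with 16 and charges the method with Week 4 visits that no method can observe. The one reservation is that 1.35 is given for activities of daily living, so the documents do not establish it for pain.

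The bias in step 5 comes from missed Week 4 visits, not missed Week 2 visits. A simple paired baseline-to-Week-4 test would carry the same bias. Rescuing the pairs dropped for a missed Week 2 visit would therefore not remove it; using the Week 2 scores of people without Week 4 does.

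Two further inferences are not supported. Cohort 2's itemised payments (25, 25 and 50 dollars at one, two and three months) leave nothing for Week 2, and a reader might conclude that this visit will be missed more often. The documents give no evidence of that, and eligibility requires willingness to attend follow-up. A reader might also compute losses over Cohort 2's five visits, but item 8 describes an analysis of three occasions, and Cohort 1 ends at Week 4.

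**Conclusion.** The concern holds in a limited form. Item 8 names a method that, in its classical form, uses only participants seen at baseline, Week 2 and Week 4, and the available text gives no other rule. With 10% of follow-up visits missed, about 16 of 20 are analysed although about 18 have baseline and Week 4. The effect on power is negligible at the plan's effect size and modest at an assumed smaller one.

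The larger issue is a possible bias in the device's favour of roughly 0.1-0.2 SD. It requires 15-25% of Week 4 visits to be missed and missingness to depend at least moderately on Week 2 relief; with weaker dependence it is smaller. The missed-visit rates, correlations and strength of selection are all assumptions. The mixed model removes the bias only if missingness depends on observed scores. The gap should be closed before analysis, because a better method is available at little cost.

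**What to change.** In Study Design item 8, replace repeated-measures ANOVA for pain with wording to this effect: *Pain scores will be analysed with a linear mixed model for repeated measures, fitted by restricted maximum likelihood to all observed scores, with visit as a categorical factor, an unstructured within-person covariance (a simpler structure if it does not converge) and Kenward-Roger degrees of freedom. The pain result is the change from baseline to Week 4 with its 95% confidence interval. Changes at Months 2 and 3 are reported within Cohort 2.* Add that missing scores are assumed missing at random given observed scores, and report the number with data at each visit.

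The Kenward-Roger adjustment is needed because, with about 20 people, unadjusted tests from an unstructured model reject too often.

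The cost is a few sentences in item 8, slightly more analysis work and possible convergence problems at this size, for which the simpler covariance is the fallback. No extra participants, visits or data are needed.

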We propose a proof of concept clinical trial to assess the validity of a novel foot offloading device (PopSole™) that allows for customized pocketing out of areas of pain, along with customized arch support and metatarsal height to optimize offloading.

An important part of recovery from foot injury (including fat injections, treatment of diabetic ulcers, wart removal, painful calluses, healing fractures) is the minimization of pressure to optimize healing. This offloading is challenging because current modalities limit patient function, work, and safety due to their bulk, weight, and attractiveness. (7) Aggressive modifications to shoe soles create asymmetry between the feet that can lead to gait instability, falls, and pelvic shifts. (8-15) We have another clinical trial to assess comparison of this device to our current standard of care method utilizing cutting metatarsal pads and adhering them to current insoles to reduce pressure on grafted areas, but this does not adequately reduce pressure on the fat grafted areas.

Our device can be used in conjunction with post-operative boots that have flat bottoms to augment them for more comfort and potentially enable earlier transition to regular shoe gear. It may be able to eliminate more bulky devices completely as PopSole™ can fit into a regular sneaker or dress shoe.

With our novel device PopSole™, we aim to expedite the recovery process, reduce pain, and reduce compensatory gait issues that could lead to falls. Patient balance and stability is a big concern with the presently available offloading modalities. Falls and injuries have been experienced by patients, especially elderly, neuropathic diabetic patients and physically challenged individuals. In addition, our device can be easily placed in a slide-on shoe for wear around the house, or in the shower.

Our primary aim of this validation project is to allow patients with foot pain to trial the device for 4 weeks to assess improvements in pain, assess fit and feel, durability, and compliance. This project will allow for modifications of the device to be made prior to future randomized studies to assess pressure and gait assessment, shear forces, and use in the diabetic population.

View: Pitt SF: Study Design

Study Design

1. Total number of subjects to be enrolled at this site (enter -1 for chart reviews, banking, registries):

20

2. Describe and explain the study design:

This is a prospective proof of concept study.

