- Manchester Foot and Ankle Disability Index to assess subject foot pain/discomfort
- Pittsburgh Foot Survey to assess subject pain, activity, life satisfaction/quality of life
- Mayo Clinical Scoring System questionnaire (MAYO) to assess subject pain, activity, and function (Investigator Rated)
- American Orthopaedic Foot and Ankle Society questionnaire (AOFAS) to assess subject pain and function (Investigator Rated)
- 2.) 2D Photographs of both feet will be performed for a visual baseline assessment of skin.
- 3.) Collection of subject's vital signs (Temp, HR, Resp., BP), medication profile, allergies, weight, BMI calculation and adverse event collection and reporting.
- 4.) Diary cards with instruction to start entry on the diary card 24 hours after the screening visit to continue through Visit 2 (Month 1) and be placed to study chart. The subject will be instructed to document self-assessment of the following events pertaining to the feet: Pain, Bruising, Redness of the skin, Itching, Swelling, Bleeding, Other (any concerns/issues not listed). The subject will be instructed to identify on the diary card the location, date, and day of each documented event. Unresolved events at Visit 2 will be carried over for documentation to the adverse event log.

5.) Offload Device Distribution to remain in use at all times during ambulation. Devices will be provided for both feet to maintain symmetry and gait stability between the two feet. One pair of devices will be given for use in shoe gear, and one pair will be given for use in a slide in the shower. A device instruction sheet will also be provided to the participants for reference.

48 Hour (+/- 1 Day) Phone Call

The study coordinator will call the subject 48 hours after the screening visit and eligibility determination. This phone call is to assess if there are any questions or concerns with the fit and feel of the PopSole device. If there are any issues that the subject may be experiencing the study coordinator will have an investigator or co-investigator reach out to the subject. The coordinator will be working off of a phone script, to ensure that all aspects of wearing the device have been addressed.

Follow up Visits:

Visit 1 (Week 2) with (+/- 7days) study window:

This visit will take approximately 1 hour and will take place at the Isaly's Medical Building- UPMC Aesthetic Surgery Center and/or UPMC Lemieux Sports Medicine Complex with the physician investigator and research team.

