Irritation of feet by the device. Difficultly of foot fitting in shoe with the device. The device may not offload the appropriate area and a new device may need to be provided, or modifications to the device may need to be made. Slippage of the device in foot gear. Feeling of asymmetry or one foot being higher than the other.

4. Other Risks:

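### The diary is framed around the feet and names no slip, fall, insole-slippage or asymmetry item, so falls appear to depend on unprompted recall

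*Combined protocol and SAP*

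**What the plan says.** **Diary** (Research Activities, screening research procedures, item 4, same wording in Cohorts 1 and 2). Participants are to "document self-assessment of the following events pertaining to the feet: Pain, Bruising, Redness of the skin, Itching, Swelling, Bleeding". The list then closes with an open Other line for anything it does not name. The same item says that events still unresolved at Visit 2 are carried to the adverse event log. It gives no rule for events that have resolved.

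**Listed device risks** (Risk and Benefits, item 1, and the Offloading Devices risk form at the end). The first two are "Irritation of feet by the device. Difficultly of foot fitting in shoe with the device". The third is that the wrong area is offloaded, so that the device has to be replaced or altered. The last two are "Slippage of the device in foot gear. Feeling of asymmetry or one foot being higher than the other".

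**How the device is used** (Research Activities, item 5 of the same list). It is worn whenever the participant walks, on both feet for symmetry and gait stability. Besides the pair for shoes, "one pair will be given for use in a slide in the shower".

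**Why stability matters to the sponsor** (Study Aims, item 2). Reducing compensatory gait problems that could lead to falls is given as an aim of this device. The same paragraph raises balance as a concern with existing offloading methods and adds: "Falls and injuries have been experienced by patients, especially elderly, neuropathic diabetic patients and physically challenged individuals".

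**Other collection routes** (Research Activities, both cohorts). Each follow-up visit has open adverse event collection, not restricted to the feet, with medical record review, and a device survey on fit and feel. Both cohorts have a scripted 48-hour call, and Cohort 2 has further calls at Weeks 6 and 10. Difficulty in using the device is a secondary outcome (Study Design, item 3).

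**The concern.** The diary is the only instrument described as being filled in by the participant between visits. Its named items are skin and soft-tissue symptoms plus pain. Someone who slips in the shower, or whose insole shifts in the shoe, sees no line for it. The lead-in also points them to foot events, so they may not think to write a fall under Other.

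Stability in use is part of the stated rationale, and the study is meant to guide changes to the device before randomised studies that include use in people with diabetes (Study Aims, item 2). If slips and falls are collected only when a participant happens to mention them, a low count is hard to interpret. It could mean few events or few reports. The monthly review by the study team (Data Safety and Monitoring, item 1) would have the same difficulty.

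**Working it through.** The plan gives no figure on this point. The check sets each listed risk, and falls, against every collection route in the text.

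| Event | Named diary item | Other routes in the text |
|---|---|---|
| Irritation of the feet | Yes (redness, itching) | Other line, visit adverse event collection |
| Difficulty fitting in the shoe | No | Other line, fit-and-feel survey and calls |
| Wrong area offloaded | No (pain might reflect it) | Other line, survey and calls, adverse event collection |
| Insole slippage | No | Other line, survey and calls |
| Feeling of asymmetry | No | Other line, survey and calls |
| Slip, trip or fall (not a listed device risk) | No | Other line if the participant thinks it belongs there, adverse event collection |

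1. Named diary items directly cover 1 of the 5 listed risks.
2. Listed risks with no route at all: 0 of 5. Falls also have a route.
3. Slippage, asymmetry and shoe fit are matters of fit and feel, so the survey and calls plausibly ask about them. Falls are not described as part of any of these, which leaves the open adverse event question.
4. Recall period for that question. At Visits 1 and 2 it runs from the preceding visit, nominally 2 weeks each. In Cohort 2, Visits 3 and 4 (Weeks 8 and 12) word it as since follow-up Visit 1 (Week 2). By schedule that is 8 − 2 = 6 weeks and 12 − 2 = 10 weeks. Counting from the preceding visit would give 8 − 4 = 4 weeks and 12 − 8 = 4 weeks.
5. Route from diary to log. A slip or fall is momentary. Written under Other and over by Visit 2, it does not meet the carry-over condition, so it reaches the log only if it is also raised at the visit.
6. Diary period. In Cohort 2 the instruction ends diary entry at Visit 2 (Month 1), while follow-up runs to Week 12. Cards are handed out again at Visit 2, but Visit 3 lists collection only. Diary cover for the later weeks is therefore unclear.
7. Examination. Gait is evaluated at screening. Follow-up visits describe only a limited physical exam with a foot exam, so no repeat gait evaluation is described that would make up for the missing prompt.

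**The case against.** The strongest reply is that the diary is one route among several. The Other line is open to any concern. Each visit collects problems and symptoms of every kind, including unscheduled hospital or primary care visits, with record review. The call scripts are meant to cover every aspect of wearing the device. The diary card, survey and scripts are not reproduced, so prompts for slips or falls may already exist. All of this stands. A reader might infer that most of the device's risks go unrecorded prospectively. The documents do not support that, since every listed risk has at least one route.

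It is also fair to say that the falls passage is mainly about existing offloading methods and higher-risk patients. Neuropathy and concurrent leg injury affecting gait are exclusions here, devices go on both feet, and falls are not a listed device risk. That lowers the expected number of falls. It does not remove the interest in counting them, because fewer gait problems that could lead to falls is claimed for this device.

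A reader might want to size the loss from an assumed fall rate among the 20 subjects, or argue that one missed event would change the conclusion. Neither is supported. The documents give no such rate. The chance that an event occurs is not the chance that the existing routes miss it. No stability endpoint or threshold is stated for a single event to overturn.

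**Conclusion.** The point holds in a limited form. The text describes no specific, structured prompt for slips and falls, and no named diary line for insole slippage or asymmetry. Falls and near-falls therefore appear to depend on unprompted recall, over 6 and 10 weeks by the wording at Cohort 2 Visits 3 and 4. The diary's carry-over rule would not bring a resolved event into the adverse event log.

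This is a minor weakness in data collection, not an absence of safety data. The conclusion assumes that the forms not shown contain no such prompts. If they do, only the diary wording, the recall wording and the carry-over rule remain to be tidied. How many events would be missed cannot be estimated from the documents.

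**What to change.** In both cohorts:

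- Widen the diary lead-in so that it reads: *pertaining to the feet, or to walking and balance while wearing the device*.
- Add three tick lines: slip, trip or fall (in shoe or in shower slide); insole slipped in the shoe; one foot felt higher than the other.
- Ask the same lines at the existing phone calls and visits, unless the survey and scripts already do.
- Report the number of participants with each event.

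This needs a revised card, and revised scripts where required, through an IRB modification. It adds no visits. The downside is a slightly longer card and more minor events reported.
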